8.1.5 Clinical Investigation Plan (CIP) Deviations

8.2 General Methodology

Data analysis will be performed on the final frozen set of data. Data will be read only for the analysis, and data will not be modified during analysis. Analysis code will be written, appropriately documented, and version controlled. Analysis code will be kept together with the data analysis. Analysis code will be validated before final analysis. Missing data will be included in the analysis. No imputation of missing data will be done.

Data will be displayed graphically as single or multiple (for subgroups) box plots.

All statistical analyses will be performed using R – language and environment for statistical programming and graphics (version 3.X) or alternatively other accepted statistical software.

Subject data listings and tabular and graphical presentations of analysis results will be provided.

Analysis of all safety related data, including study deviations and adverse events will be based on the “intent to treat” (ITT) principle and dataset.

Analysis of all primary, secondary objectives will be done on the per protocol data set; patient data will be summarized for the per protocol data set as well.

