10.6. Deviation Handling

A protocol deviation is an event where the investigator or investigation site personnel did not conduct the clinical study according to the CIP or CTA. The investigator is not allowed to deviate from the above mentioned documents except with prior approval and under emergency circumstances. All deviations shall be documented and explained, regardless the reason for the deviation.

At the minimum, the following items will be considered as Protocol Deviations:

- Subject Informed Consent process not performed in the correct way (e.g. wrong ICF version used);
- Inclusion/Exclusion criteria violation;
- Not performed Protocol Required Data Collection/Testing

All the Protocol Deviations will be reviewed and classified by the clinical study team and appropriate actions will be determined, including any associated EC and regulatory reporting requirements, if applicable. The clinical study team will review a comprehensive summary of deviations at least on a quarterly basis to decide if measures must be taken to avoid recurrence of deviations.

Medtronic will assess the significance of all deviations and evaluate the need to amend the CIP or to early terminate the investigation, in accordance with Medtronic SOPs.

The investigator shall obtain documented approval from Medtronic, before implementation, for any change in- or deviation from the CIP. In case of study deviations that can affect the subject's rights, safety and well-being or the scientific integrity of the clinical study, approval from the EC and regulatory authority must also be obtained before implementation. The investigator shall timely contact the Clinical Study Manager for review of the proposed change/deviation.

Prior approval is not always realistic in situations where unforeseen circumstances are beyond the investigator's control. However, also in these cases, the event is considered a deviation, and shall be reported.

In any emergency situation the investigator shall exercise his/her judgment to safeguard the subject's interest. Such deviations from the CIP do not require the prior approval of Medtronic. The investigator shall report the deviation as soon as possible to Medtronic and the reviewing EC, if applicable. Medtronic will inform the regulatory authorities, if required.

All the Protocol Deviations will be documented in the appropriate CRFs.

The investigator shall adhere to EC requirements and procedures for reporting study deviations.

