10.7. Subject Withdrawal or Discontinuation

If a subject is withdrawn from the clinical study, the reason for withdrawal shall be recorded in the study exit form and in the subject's hospital record. If discontinuation is because of safety the subject shall be asked to be followed for collecting safety data outside the clinical study.

Possible reasons for withdrawn from the study are:

- Subject withdrew consent;

- Investigator withdrew subject from the study for medical reasons;
- Investigator withdrew subject from the study due to inclusion/exclusion criteria not met.

Subjects withdrawn might be replaced in case the number of dropouts will significantly affect the possibility to properly address study objectives.

Since AF septal pacing will only be used to collect data only for the time of the clinical study, there is no specific medical care that will be provided to the subjects after the clinical study will be completed or in case of subject withdrawal.

11. Risks and Benefits

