14.2. Patients sets considered for the analysis

The analysis set will include all enrolled patients matching inclusion/exclusion criteria (Intention to Treat).

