8.1.3 Intention to Treat Dataset

The “intention to treat” (ITT) dataset will be the primary dataset for patient baseline and safety related reporting. All patients that meet the study inclusion and exclusion criteria, that signed the informed consent, and underwent the clinically indicated ablation procedure are part of the intention to treat dataset. Patients that did not undergo the ablation procedure are not part of the intention to treat dataset.

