8.1.4 Per Protocol Dataset

The “per protocol” (PP) dataset will be the primary dataset for the analysis of the primary and secondary study objective. All patients where the septal lead was placed, and the septal pacing threshold test was performed are part of the per protocol dataset. Patients remain in the per protocol dataset if no high rate overdrive pacing was performed.

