8.8 Safety Evaluation

All adverse events (AE) will be reported. Summary description of all adverse event will be provided for each reported AE.

For serious adverse events (SAE), device related adverse events, and unanticipated adverse device effects (UADE) a detailed description will be provided.

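### The SAP analyses adverse events and deviations in a set that admits only eligible, ablated patients, so eligibility violations cannot appear in it and an ineligible paced subject counts for the primary objective but not for safety

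*SAP*

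**What the plan says.** SAP 8.2 sets the population for safety: "Analysis of all safety related data, including study deviations and adverse events will be based on the" ITT principle and dataset. SAP 8.1.3 defines that dataset as "All patients that meet the study inclusion and exclusion criteria, that signed the informed consent, and underwent the clinically indicated ablation procedure" and adds: "Patients that did not undergo the ablation procedure are not part of the intention to treat dataset". It also calls this the primary dataset for baseline and safety reporting.

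SAP 8.1.4 defines the per-protocol set differently: "All patients where the septal lead was placed, and the septal pacing threshold test was performed are part of the per protocol dataset". It sets no eligibility condition and does not say that the set lies within the ITT set. SAP 8.2 and 8.7 use the per-protocol set for the primary and secondary objectives.

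SAP 8.8 says "All adverse events (AE) will be reported" and names no population.

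Protocol 10.6 includes "Inclusion/Exclusion criteria violation" in its minimum list of protocol deviations. Protocol 10.7 gives as a possible reason for withdrawal: "Investigator withdrew subject from the study due to inclusion/exclusion criteria not met". Protocol 14.2 defines a single set: "The analysis set will include all enrolled patients matching inclusion/exclusion criteria (Intention to Treat").

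**The concern.** A safety and deviation set should contain the people who were put at risk by the study and the people in whom the protocol was broken. The SAP's ITT set is instead filtered on eligibility, and an eligibility breach is itself one of the deviations to be summarised. A deviation summary made on this set would show no such breach even if some occurred.

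The primary objective uses a different filter. Pacing data from an ineligible subject can support the feasibility conclusion while that subject's adverse events fall outside the safety analysis. With about 15 subjects planned, one person is a visible part of the safety experience. Because 8.2 and 8.8 can be read as giving different populations, two analysts following the SAP could produce different safety reports.

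**Working it through.** The plan gives no figure to reproduce: there is no hypothesis and no sample size calculation (SAP section 7). The check applies the membership rules.

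**Rules**

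- SAP ITT (8.1.3) = eligible AND consented AND ablated.
- SAP per protocol (8.1.4) = septal lead placed AND threshold test done.
- Protocol 14.2 set = enrolled AND eligible, where enrolled means the consent form was signed (Protocol 8.2).

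The study steps follow pulmonary vein isolation (Protocol section 10), so the table leaves out threshold testing without ablation. All subjects shown have consented.

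| Subject | SAP ITT (safety, deviations) | SAP per protocol (objectives) | Protocol 14.2 |
|---|---|---|---|
| Eligible, ablated, tested | in | in | in |
| Eligible, ablated, not tested | in | out | in |
| Eligible, not ablated | out | out | in |
| Ineligible, ablated, tested | **out** | **in** | out |
| Ineligible, ablated, not tested | out | out | out |
| Ineligible, not ablated | out | out | out |

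**What follows**

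1. Every subject with an eligibility violation is in one of the last three rows, and all three are outside the ITT set. The count of such violations in the ITT-based analysis is 0 by construction.
2. The fourth row is the mismatch: counted for the primary objective, not counted for safety.
3. The third row shows that an event in an eligible, consented subject who was never ablated is outside the analysis. An event before or during ablation in an eligible subject who is then ablated remains in.
4. Protocol 14.2 shares the eligibility restriction but has no ablation condition. It matches neither SAP set.

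**Illustration of size**

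Assumption: 15 subjects are tested, exactly one of them is ineligible, and that subject has the only adverse event. Exact (Clopper-Pearson) 95% intervals are used; for zero events in n, the upper limit is 1 − 0.025^(1/n).

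- All 15 counted: 1/15 = 6.7% (0.2% to 31.9%).
- SAP ITT: 15 − 1 = 14 subjects, 0/14 = 0%; upper limit 1 − 0.025^(1/14) = 23.2%.

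If that subject is also replaced, as Protocol 8.1 and 10.7 allow in some circumstances:

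- All 16 counted: 1/16 = 6.3% (0.2% to 30.2%).
- SAP ITT: 0/15 = 0%; upper limit 1 − 0.025^(1/15) = 21.8%.

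With k ineligible tested subjects among 15, the safety denominator is 15 − k (14, 13, 12 for k = 1, 2, 3) while the per-protocol denominator stays at 15. The range of k is an assumption.

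**The case against.** The strongest reply is that no event need be lost. SAP 8.8 is the dedicated safety section, and a promise covering all adverse events is most naturally read as excluding nobody. SAP 8.1.3 calls ITT the primary dataset for safety, which does not make it the only one. Violations can also be seen elsewhere. Protocol 10.6 requires every deviation to go on a CRF and a comprehensive summary to be reviewed at least quarterly. The SAP's baseline data table holds each inclusion and exclusion item per subject, listings are planned, and disposition starts from all enrolled. Patients are screened against the criteria before consent, so the case should be uncommon. The SAP plans descriptions of adverse events and has no table shell for their incidence, so the contrast of 1/15 with 0/14 matches no planned output. The per-protocol set may have been meant to lie within the eligible population. Leaving out patients who were never ablated resembles an exposure-based safety set, which is defensible.

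Much of this stands as a limit on the consequences. Data capture is not at fault, the fractions are illustrative, and if nesting was intended the mismatch with the per-protocol set disappears once the SAP says so. It does not repair the rule. Section 8.8 names no population and does not override 8.2: if it means every event the two sections conflict, and if it follows 8.2 the omission remains. The other sources record or list violations but do not change the set prescribed for analysing them. An exposure-based choice could justify omitting patients who were never ablated. It cannot justify omitting an ineligible patient who was paced.

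**Conclusion.** The concern holds on the text as written, and the plan should be changed. Eligibility violations are structurally zero in the analysis that 8.2 prescribes, and this does not depend on any assumption about the data. The mismatch between the safety and primary-objective populations follows from the literal definitions, on the reading that the per-protocol set is not nested in ITT; nothing in the SAP says that it is. Adverse events in consented subjects who were never ablated are also outside the set, and 8.2 and 8.8 need to be reconciled on any reading.

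The practical size depends on how many ineligible subjects are paced, which the documents do not give. Under the one-subject assumption, the safety analysis moves from one event in 15 to none in 14. The study is descriptive, so no test or error rate is affected; what is at stake is whether the safety and deviation account is complete.

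**What to change.** - In SAP 8.1.3 and 8.2, replace the ITT set for adverse events, device deficiencies and deviations with all subjects who signed the consent form, regardless of eligibility or ablation. Flag those in whom any study-specific step (septal catheter placement or pacing) began, so that the exposure-based view can be shown alongside.
- In SAP 8.8, name this set as the one used.
- In SAP 8.1.4, state whether the per-protocol set requires eligibility.
- Keep the eligible, ablated set for the baseline description.
- Align Protocol 14.2 by amendment, or record and justify the change under Protocol 14.8.

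The cost is wording in these sections. No new data are needed: Protocol 10.1 (Table 2) already has adverse events, device deficiencies and deviations collected throughout the study, and the SAP's baseline data table already holds consent and every eligibility item. The report may show a few more events or deviations.

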8.2.1 Analysis of Baseline Data

All clinically relevant baseline variables will be tabulated and reported. Categorical variables will be reported using counts and percentages, and continuous variables will be reported by giving the number of known values, the mean, standard deviation, median, minimum and maximum values. Number of missing data for continuous variables will be reported as well.

8.3 Handling of Missing, Unused, and Spurious Data and Dropouts

Missing data will be excluded from the statistical analysis. Missing data will be reported for each variable. No imputation method for missing data is planned.

8.4 Adjustments for Multiple Comparisons

The study is descriptive in nature, and statistical reporting will be descriptive. There are several groups of interest to look at, such as unipolar / bipolar stimulation, different leads, different centers, ..., etc. No statistical comparison is planned between groups, and thus no adjustment for multiple comparison is required.

8.5 Demographic and Other Baseline Characteristics

Demographic and baseline characteristics are divided in continuous and categorical data that will be summarized in table format.

- Age, Gender, Weight, Height, right and left atrial volume index are considered continuous data for which count of data, count of missing data, mean, median, standard deviation, minimal and maximal values will be computed.
- Atrial arrhythmia, Sinus node dysfunction, Ventricular Arrhythmia, and AV-junctional arrhythmia and blocks are instead categorical variables for which count of data and count of missing data, number and percentage per category will be calculated..

8.6 Treatment Characteristics

Procedure data will be summarized in table format as count of data, count of missing data, mean, median, standard deviation, minimal and maximal values for continuous variables, and count of data and count of missing data, number and percentage per category, for categorical data.

The following continuous data will be summarized and reported as described above:

- Current Medication at the start of the procedure
- Medication given during procedure

The following categorical variables will be summarized and described as above:

- Type of Anesthesia
 - General
 - Sedation
- Type of AF treated:
 - Paroxysmal
 - Persistent
 - Permanent
- Type of AF procedure
 - Initial
 - Redo
- Outcome of PVI ablation
- Tabulation of devices used for atrial septal pacing.

8.7 Evaluation of Objectives

The primary objective is purely descriptive. The per protocol dataset will be used for evaluation of the primary and secondary objective. Reporting on primary and secondary objective will be initially done for the full protocol dataset. Pre-defined subgroups will be described including the following: Per Center analysis, per initial arrhythmia, per septal lead, per patient mode (unipolar vs. bipolar).

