One reason why clinical studies are often non-conclusive, could be that they focus on AF frequency and burden, but few of them are aimed at evaluating the effect of AF pacing on the atrial tissue.⁹ More detail can be found in animal and human mapping experiments: although termination of AF by rapid pacing was not observed, the possibility of creating an area of local capture of the atrial tissue by rapid pacing of AF has been demonstrated.¹⁰⁻¹⁴ To overcome the limitations of human and animal experiments, a computer model of AF has been used to systematically simulate all existing ATP algorithms on AF and test all pacing locations.¹⁵ This systematic model-based testing of site rapid pacing of AF revealed that the septum was the only pacing site that yielded sporadic AF capture episodes in both atria, but this in general did not result in AF termination or permanent changes in AF patterns. Based on this result, a new dual-stage septal pacing has been developed in the computer model: rapid pacing was applied from the septal area following a dual-stage scheme: 1) rapid pacing for 10-30 s at pacing intervals 62-70% of AF cycle length (AFCL), 2) slow pacing for 1.5 s at 180% AFCL, initiated by a single stimulus at 130% AFCL.¹⁶ The proposed septal pacing algorithm could suppress AF reentries in a more robust way than classical single site rapid pacing and at an optimal pacing cycle length (64% AFCL) up to 29% of AF termination was observed in the computer model¹⁶. Septal pacing of AF is therefore proposed here as a simple and attractive approach since it may produce simultaneous bi-atrial stimulation using a single lead, without the need of complex methods for synchronizing multiple pacing sites.

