8.1. Study Population

Approximately 15 subjects suffering of either persistent and paroxysmal Atrial Fibrillation, indicated for ablation of the pulmonary vein will be enrolled in the study. No control group will be used for this study. The study is planned to be conducted at up to 3 centers in Europe.

In case of missing data of enrolled subject would significantly affect the possibility to properly address study objectives the subject will be replaced in order to have at least 15 complete analyzable subjects' datasets to analyze atrial septal pacing lead stability.

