5.2 Secondary Objectives

The secondary objectives of this study are:

- Localized Atrial Capture: evaluate if during the rapid pacing phase of the two-stage septal pacing scheme (rapid pacing followed by a step-wise transition to slow-pacing) from multiple electrodes on the interatrial septum, local atrial capture can be observed during atrial fibrillation.
- AF Termination Scheme: evaluate if AF termination can be obtained using a dual-stage septal pacing scheme (rapid pacing followed by a step-wise transition to slow-pacing) from multiple electrodes on the interatrial septum.

6. Investigation Plan

The AF Septal Pacing study is a non-randomized, non-controlled, acute, single-arm research study that will be conducted in up to three European centers.

Approximately 15 subjects with AF indicated for ablation of the pulmonary vein will be enrolled in the study. Participants will attend the Baseline visit and the Procedure visit that can occur on the same day. Since it is an acute study, no follow-up visit will occur. The research procedure will be performed during an already scheduled ablation procedure.

The point of enrollment is the time when subject signs and dates the Informed Consent Form (ICF). At that point, the subject is considered included in the study.

Selection of subjects, treatment of subjects, and evaluation of study data are potential sources of bias. Methods incorporated in the study design to minimize potential bias include (but are not limited to):

- Patients will be screened to confirm eligibility for enrollment in accordance to the inclusion/exclusion criteria.
- Subject demographics will be collected at baseline on possible differences that may affect the primary objective.
- All study clinicians, participating site personnel, and Medtronic personnel will be trained on their respective pertinent role of the study using standardized training materials.

No control group, no randomization and no blinding will be used in this Study.

Clinical Study Flowchart is summarized in Figure 2:

[figure not shown]

Figure2: Standard ablation procedure (left side) and experimental procedure (right side, yellow boxes) performed during standard procedures.

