6.2 Exclusion Criteria

None of the below exclusion criteria must be met:

- Patients under 18 years or over 80 years old.
- Women who are currently pregnant or have a positive pregnancy test.
- Patients with an implantable cardiac device
- Patients who already underwent an AF septal ablation procedure.

7. Determination of Sample Size

As this is a feasibility study, no formal statistical hypotheses are being tested and no sample size calculation was performed.

8. Statistical Methods

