8.7.1 Primary Objective

The primary objective of the study is to evaluate the feasibility to obtain a stable position of a ring of stimulation electrodes on the interatrial septum (stability performance).

Specifically, this primary objective of stable position of a ring of stimulation electrodes on the atrial septum also includes pacing threshold, pacing impedance, stability criterion and safety criterion variables. These data will be summarized in table format as count of data, count of missing data, mean, median, standard deviation, minimal and maximal values for continuous variables, and count of data and count of missing data, number and percentage per category, for categorical data.

∴

Description of stability performance assessed on *per patient basis* includes:

- Description of overall stability criterion (pacing threshold < 10 mA) (categorical variable)
- Description of the number of electrode pairs reaching the stability criterion;
- Description of safety criterion (no ventricular capture) (categorical variable)
- Description of the number of electrode pairs reaching the safety criterion

Description of stability performance assessed on *electrode pair basis*:

- Description of the pacing threshold (continuous variable)
- Description of the pacing impedance (continuous variable)
- Description of stability criterion (pacing threshold < 10 mA) (categorical variable)
- Description of safety criterion (ventricular capture) (categorical variable)

○

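### Yes/no outcomes from about 15 subjects should carry exact subject-level intervals, and electrode-pair tables should show the number of patients

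*SAP*

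**What the plan says.** The study is a single-arm feasibility study. SAP section 6 states: "Approximately 15 subjects with AF indicated for ablation of the pulmonary vein will be enrolled in the study". Protocol 8.1 allows replacement of subjects "in order to have at least 15 complete analyzable subjects' datasets to analyze atrial septal pacing lead stability". SAP section 7 says that "no formal statistical hypotheses are being tested and no sample size calculation was performed", and SAP 8.4 adds: "The study is descriptive in nature, and statistical reporting will be descriptive". SAP 8.7 repeats this for the main aim: "The primary objective is purely descriptive".

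SAP 8.7.1 summarises continuous variables by "count of data, count of missing data, mean, median, standard deviation, minimal and maximal values for continuous variables". Categorical variables get a count, a missing count, and a number and percentage per category. Stability and the ventricular-capture criterion are described first per patient, including the number of electrode pairs that qualify, and then per electrode pair. The electrode-pair list includes "Description of the pacing threshold (continuous variable)" and the yes/no stability and safety criteria. SAP 8.7.2 reports AF termination as a count and frequency without naming the unit; Protocol 5.2.2 counts subjects. The Table 2 shell in the SAP appendix has columns for data count, missing, yes and no, but none for the number of patients or for precision.

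**The concern.** The documents ask questions that reach beyond the sample. Is a stable ring position feasible? Can local capture be observed? Do termination mechanisms and efficacies like the model's occur in humans? A bare percentage from about 15 people does not show how far it answers them. A result of 15/15 invites the reading that placement always works, and a result of 0 terminations that the scheme never works. Neither follows.

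The electrode-pair rows add a second problem. Electrodes on one ring share a patient, a catheter and a placement. A data count of electrodes or pairs, with no patient count beside it, suggests more information than there is. The subgroup descriptions planned in SAP 8.7 and 8.7.2 make the numbers smaller still.

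**Working it through.** **Plan's own figure.** There is none to reproduce: no sample size, power or precision calculation was made.

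**Inputs.** About 15 subjects (SAP section 6; Protocol 8.1). Four septal electrodes stimulated together (Protocol section 10 and 10.3), matching the four stimulation pairs in SAP Table 4. Assumptions not in the documents: a two-sided 95% level, the intraclass correlation (ICC), and any tested denominator below 15.

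**Step 1: subject-level intervals.** For x of n, the Clopper-Pearson limits are: lower = Beta quantile (0.025; x, n−x+1), upper = Beta quantile (0.975; x+1, n−x). At the extremes these reduce to 0.025^(1/n) as the lower limit for n/n, and 1 − 0.025^(1/n) as the upper limit for 0/n. For n = 15, 0.025^(1/15) = 0.782.

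| Result | Percentage | Exact 95% interval |
|---|---|---|
| 15/15 | 100% | 78.2% to 100% |
| 14/15 | 93.3% | 68.1% to 99.8% |
| 12/15 | 80.0% | 51.9% to 95.7% |
| 8/15 | 53.3% | 26.6% to 78.7% |
| 1/15 | 6.7% | 0.2% to 31.9% |
| 0/15 | 0% | 0% to 21.8% |

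In a subgroup of five (an illustration), 5/5 has a lower limit of 0.025^(1/5) = 47.8%.

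**Step 2: the denominator.** SAP 8.1.4 keeps patients in the per protocol set when no high-rate overdrive pacing was done. Protocol 5.2.2 and 10.3 make slow pacing conditional on feasibility. The replacement rule in Protocol 8.1 secures complete data for stability, not for pacing during AF. The number actually tested for capture or termination may therefore be below 15. If it were 12, the upper limit for zero events would be 26.5%; if 10, 30.8%. SAP 8.2 says that missing data are included and SAP 8.3 that they are excluded, so the denominator is not settled there either.

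**Step 3: electrodes within patients.** Design effect = 1 + (m − 1) × ICC, and effective size = 15m divided by the design effect. With m = 4 there are 15 × 4 = 60 observations:

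- ICC 0.2: 60 / 1.6 = 37.5, about 38
- ICC 0.3: 60 / 1.9 = 31.6, about 32
- ICC 0.5: 60 / 2.5 = 24
- ICC 1: 60 / 4 = 15

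At 80% observed, treating 48/60 as independent gives 67.7% to 89.2%. The same percentage at the effective size gives 62.0% to 92.0% at ICC 0.3 and 58.8% to 93.4% at ICC 0.5.

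If all ten electrodes were counted singly (SAP Table 3B codes electrodes 1 to 10), there would be 150 observations, with effective size 150 / 2.8 = 54 at ICC 0.2 and 150 / 5.5 = 27 at ICC 0.5. That is a ceiling. SAP 8.7.1 analyses pairs.

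**The case against.** The strongest reply is that the plan does what it declares. It disclaims hypotheses, calls itself descriptive and prints data counts beside percentages. It also gives more than counts and percentages: continuous variables get mean, median, standard deviation and range, and box plots and subject listings are planned. Per-patient stability summaries come first, so the electrode-pair tables are not the only view. Correlation does not spoil an electrode percentage as a description; it matters once precision is claimed or inferred. All of this stands, and it makes the point an improvement in reporting. It does not remove the gap, because an interval is not a test and a plan without hypotheses can still state precision.

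A reader might go further and infer that the trial can confirm or refute the model's rate, since Protocol 4.1 reports that "up to 29% of AF termination was observed in the computer model", and 0/15 has an upper limit below 29% while 0/10 does not. The documents do not support that use. The figure is a best value at one optimal cycle length, and neither document makes it a benchmark. The trial applies several cycle lengths per subject, delivers slow pacing only where feasible, and under SAP 8.7.2 counts conversion to a regular atrial tachycardia or flutter as termination. A subject-level rate of any termination is not like for like with the simulated rate.

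A patient-cluster bootstrap is also an unsafe remedy. If every electrode qualifies, it returns 100% to 100%, which is the false certainty to be avoided.

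**Conclusion.** The point holds as a low-cost improvement, not as an error or contradiction. No precision is planned for any proportion, and about 15 subjects leave intervals roughly 20 to 50 percentage points wide: 21.8 points at 0/15 or 15/15, 43.8 at 12/15 and 52.1 at 8/15. The electrode-pair tables do not show how many patients stand behind them. Sixty observations carry the information of about 38 to 24 at ICC 0.2 to 0.5, and of 15 in the extreme case.

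The subject-level limits rest only on the binomial model and the chosen 95% level. The effective sizes rest on an assumed ICC. The 29% model figure belongs in the report as context only.

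**What to change.** In SAP 8.7.1 and 8.7.2 and the table shells:

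- Add two-sided 95% Clopper-Pearson intervals at subject level for the overall stability criterion, for any local capture (at least one electrode position) and for AF termination.
- State the rule that turns electrode results into one yes/no per subject. For capture this is a new definition, because Protocol 5.2.2 counts episodes and electrodes. For stability, say whether every electrode must qualify, as Protocol 10.3 words it.
- Use as denominator the subjects who actually received the relevant test or pacing, and print it.
- Show the number of patients beside the number of electrode pairs, and summarise electrode-level results as per-patient proportions.
- If an electrode-level interval is shown, use a patient-clustered method that does not collapse at 0% or 100%. One option is an exact interval on the effective size, falling back to the number of patients when all or no electrodes qualify.
- If the 29% model figure is mentioned, label it as context, with no statement of pass or fail.

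The cost is a few definitions, a few lines of R and some table columns. No patients, tests or procedures are added. The drawback is that results will look less certain.
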